1.3.2.6 Echocardiographic Endpoints

Echocardiographic endpoints will be assessed by the Echocardiography Core Laboratory (ECL) and reported at baseline, discharge, 30 days, 6 months, 1 year, 2 years, and 3 years post-implantation (unless indicated).

- o TR Severity Grade
- Effective Regurgitant Orifice Area (EROA)
- Regurgitant Volume
- Regurgitation Jet Area
- Vena Contracta Width
- Proximal Isovelocity Surface Area (PISA) Radius
- o Inferior Caval Vein Diameter
- Tricuspid Annular Diameters (Antero-P and S-L)
- Tricuspid Annular area
- Tricuspid Valve Area
- Tenting Area (At baseline only)
- Tenting Distance (At baseline only)
- Tricuspid Leaflet Tethering Distance (At baseline only)
- Right Ventricular End Diastolic Dimension (RVEDD)
- Right Ventricular End Systolic Dimension (RVESD)
- o Right Ventricular Fractional Area Change
- Right Ventricular Systolic Pressure (RVSP)
- Right Atrial Volume
- Tricuspid Annular Plane Systolic Excursion (TAPSE)
- Right Ventricular Free Wall Strain
- Mean Tricuspid Valve Gradient
- Cardiac Output
- Forward Stroke Volume (Left Ventricle)
- Left Ventricular Ejection Fraction (LVEF)
- Single Leaflet Device Attachment
- o Embolization of the TVRS Clip or TVRS System components

• Tricuspid Valve Stenosis

1.3.3 Exploratory Endpoints

Right Heart Catheterization: Right heart catheter measurements at:

- Immediately before TVRS procedure: Measurements to include: right atrial a-wave/vwave, right atrial and ventricular pressures, pulmonary resistance, PA pressures and cardiac output),
- Post-procedure Right Atrial Catheterization, immediately after TVRS procedure (rightatrial a-wave/v-wave, right atrial pressure)

1.4 Analysis Populations

		-		
	-	-		
-				

2. ANALYSIS CONSIDERATIONS

2.1 Statistical Methods

Descriptive analysis will be performed to summarize baseline, echocardiographic, clinical and safety event data. Depending on the type of data (e.g., continuous or categorical), statistical methods described in the following sections will be used.

2.1.1 Descriptive Statistics for Continuous Variables

For continuous variables such as age, results will be summarized with the numbers of observations, means, and standard deviations, and, if specified in the table mockups, with quartiles, minimums, maximums, and 95% confidence intervals for the means. Differences between two groups, where specified, will be summarized with differences of the two means, and 95% confidence intervals for the difference between the means. These calculations will be done under the assumption that the data for the two arms are independent and approximately normal in distribution. The confidence interval for the difference of two means will be calculated under the assumption of unequal variances. If the asymptotic assumptions fail, then nonparametric summary statistics (medians, 25th and 75th percentiles) may be displayed as an alternative.

2.1.2 Descriptive Statistics for Categorical Variables

For categorical variables such as gender, MAE, results will be summarized with subject counts and percentages/rates, and where specified in the table mockups, with exact 95% Clopper-Pearson⁸ confidence intervals.

For effectiveness and safety endpoint(s), relative risks (i.e., the ratio of rates), confidence interval for the relative risks, the difference in rates and the confidence interval for difference in rates (using previously-described formulas), and p-values may also be presented for hypothesis generating purposes.

For the determination of event rates at time points (e.g. 30 days), the counting starts from the time of enrollment.

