	 Major Adverse Events (MAE) occurring after femoral vein puncture. MAE as listed below will be adjudicated by the Clinical Events Committee: Cardiovascular Mortality, Myocardial Infarction (MI), Stroke, New onset renal failure, Endocarditis requiring surgery Non-elective Cardio-Vascular (CV) surgery for TVRS device-related AE post-index procedure. 				
Secondary Endpoints	Acute Secondary Endpoints:				

(Version 2.0; 01 February 2018)

Echocardiography Core Laboratory (ECL) assessment of a discharge echocardiogram (30-day echocardiogram will be used if discharge echocardiogram is unavailable or uninterpretable). Subjects who die or undergo tricuspid valve surgery before discharge are an APS failure.

- Acute Device Success: Successful access, delivery of the Clip and removal of device delivery system. Successful delivery of the Clip is the deployment of the device as planned, with no additional unplanned surgery or reintervention related to the device or access procedure.
- Implant Success Rate: Successful delivery and deployment of the Clip(s) with achievement of leaflet approximation(s) and retrieval of the delivery catheter
- Total Procedure Time: defined as the time elapsed from the first of any of the following: intravascular catheter placement or trans-esophageal echocardiogram (TEE), to the removal of the last catheter and TEE
- Device Time: defined as the time the Steerable Guide Catheter is placed in the right atrium until the time the TVRS Delivery System is retracted into the Steerable Guide Catheter
- Fluoroscopy Duration: defined as the duration of exposure to fluoroscopy during the TVRS procedure
- Length of hospital stay for the index TVRS procedure
- Location to which subject was discharged (home, home health or another facility)
 - If subject discharged to another facility, length of stay at facility to which subject was discharged

Clinical Composite Endpoints:

• MAE at discharge, 30 days,1 year, 2 years and 3 years

Clinical Component Endpoints:

Clinical Endpoints at 30 days, 6 months, 1 year, 2 years and 3 years:

- Components of MAE
- All-cause mortality
- NYHA Functional Class
- Tricuspid valve surgery (including type of surgery)
- New use of any cardiac rhythm management devices (Pacemakers, Implantable Cardioverter-Defibrillator (ICD), and Cardiac Resynchronization Therapy (CRT)), including reason for intervention
- Additional TVRS intervention and reason for intervention

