3.0 CLINICAL TRIAL/INVESTIGATION FLOW AND FOLLOW-UP SCHEDULE

For screening, each subject must undergo clinical assessments and echocardiography; both transesophageal echocardiogram (TEE) and transthoracic echocardiogram (TTE) are acquired. **Figure 2** shows the overall flow of the trial.

[figure not shown]
(Version 2.0; 01 February 2018)

Subjects will be screened for study eligibility by the Investigator as well as the Site Heart Team per the inclusion and exclusion criteria. A cardiac surgeon and an echo specialist will assess subjects for eligibility criteria for surgical appropriateness and echocardiography, respectively.

The TTE and TEE will be submitted to the Echocardiography Core Laboratory (ECL) for assessment of
TR severity. Once the subject is deemed by the ECL to meet TR severity and the subject meets all
inclusion and none of the exclusion criteria, an Independent Eligibility Committee
will review pertinent medical history to make the final
determination regarding eligibility of prospective subjects, including eligibility of tricuspid valve anatomy
(see APPENDIX IX). Once the Eligibility Committee confirms that the subject is eligible for the TVRS
procedure in the trial, the subject may be scheduled for the TVRS procedure.

Enrolled subjects will undergo clinical evaluations at baseline, discharge, 30 days, 6 months, 1 year, 2 years, and 3 years following the TVRS procedure (see **Table 2** for Clinical Evaluation Schedule).

(Version 2.0; 01 February 2018)

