5.0 SUBJECT SELECTION AND WITHDRAWAL

5.1 Subject Population

The trial will enroll a minimum of 85 subjects who will undergo the TVRS procedure. This trial will enroll male and female subjects from the heart failure population who have at least moderate grade TR, and satisfy the general and echocardiographic inclusion and exclusion criteria. Subjects must sign and date the informed consent prior to conducting any trial-specific procedures not considered standard of care.

TRILUMINATE Trial

(Version 2.0; 01 February 2018)

Any patient data transmitted from their institution to the ECL or Sponsor must have prior signed and dated informed consent.

Assessment for general eligibility criteria is based on medical records of the site and interview with a candidate subject. If some of the clinical and laboratory tests are not included in site standard tests, they must be done, but after signed and dated informed consent is obtained. Subjects must meet ALL of the inclusion criteria to be considered for the clinical evaluation. If ANY of the exclusion criteria are met, the subject is excluded from the clinical evaluation and will not qualify for the TVRS procedure.

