5.3 Subject Enrollment

Subjects are enrolled in the TRILUMINATE Trial upon signing and dating the informed consent form.

^{*} For Switzerland Only: A legally authorized representative will not be allowed to provide informed consent for a patient.

³⁰ Braun D, Nabauer M, Orban M, Orban M, Gross L, Englmaier A, Rösler D, Mehilli J, Bauer A, Hagl C, Massberg S, Hausleiter J. Transcatheter treatment of severe tricuspid regurgitation using the edge-to-edge repair technique. EuroIntervention, 2017 Feb 3:12(15):e1837-e1844.

³¹ Nickenig G, Kowalski M, Hausleiter J, Braun D, Schofer J, Yzeiraj E, Rudolph V, Friedrichs K, Maisano F, Taramasso M, Fam NP, Bianchi G, Bedogni F, Denti P, Alfieri O, Latib A, Colombo A, Hammerstingl C, Schueler R. Transcatheter Treatment of Severe Tricuspid Regurgitation with the Edge-to-Edge: MitraClip Technique. Circulation. 2017 Mar 23.

(Version 2.0; 01 February 2018)

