6.5 Follow-up for All Subjects

Required clinical follow-up will be performed at the following intervals for all subjects with TVRS procedure attempt, regardless of whether a TVRS Clip was successfully implanted:

- Discharge post-TVRS procedure
- 30 days follow-up office visit (this visit must be conducted even if subject is in hospital)
- 6 months
 follow up office visit
- 1 year follow up office visit
- 2 years3 yearsfollow up office visitfollow up office visit
- Discontinuation

Follow-up visits will be calculated from the date of the Procedure. Follow-up assessments can be performed at any point in the window, and should be conducted, whenever possible, by the same individual who performed the baseline tests. The subject should be followed at the investigational site where the subject was enrolled, and may be followed at another investigational site only with prior agreement from that site's Investigator and from the Sponsor.

During the physical examination at the 30-day follow-up clinic visit, the implanting or treating investigator shall examine the integrity of the TVRS Clip. At the 30-day, 6-month, 1-year, 2-year and 3-year follow-up visits, all subjects must be examined by the Investigator. Subjects must continue to take baseline medications without change during follow-up, unless clinically (medically) necessary. If there are any cardiovascular medication changes (including dosage changes), these changes should be documented on the electronic case report form. In general, neurohormonal antagonists should not be changed. Subjects implanted with the TVRS Clip must also be evaluated for device integrity. Required tests and procedures outlined below must be completed. Timing of specific tests will follow the Clinical Evaluation Schedule (**Table 2**) outlined above. All visits and tests must be completed even if the subject is in hospital.

- 12-lead FCG
- Blood draw

(Version 2.0; 01 February 2018)

- Brief physical exam including vital signs (weight, heart rate, blood pressure and temperature)
- Echocardiogram TTE at all follow-up visits and TEE at 30-day visit only
- Modified Rankin Scale (Assessment of mRS should additionally be done at 90 days after onset of stroke)
- 6-Minute Walk Test (6MWT) (excluding discharge and 30-day follow-up visit) See

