1.3.2.5 Device or Procedure-Related Adverse Events

Prevalence of Device or Procedure-Related Adverse Events

Device or procedure-related adverse events will be broken down into those that occur within 30 days of the procedure and those that occur after 30 days of the procedure. Examples of device-related adverse events are:

- Myocardial perforation
- Damage to tricuspid valve apparatus
- o Access Site bleeding requiring surgery
- Non-vascular bleeding

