2.1.4 Survival Analyses

Survival analysis will be conducted to analyze time-to-event variables, e.g. all-cause mortality. For analyses of clinical events (e.g. MAE) beyond 30-day follow-up, Kaplan-Meier¹¹ estimate will be utilized.

Subjects without events will be censored at their last known event-free time point. Survival curves will be constructed using Kaplan-Meier estimates. Summary tables for endpoints will include failure rates (Kaplan-Meier estimates), and confidence interval for the failure rates.

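### SAP 2.1.2 counts event rates from enrollment (consent) while the endpoints and visits run from the procedure, and the 6-month MAE test has no visible time origin

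*SAP*

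**What the plan says.** SAP 2.1.2, which covers categorical variables and names MAE as an example, sets the clock: "For the determination of event rates at time points (e.g. 30 days), the counting starts from the time of enrollment".

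Protocol 5.3 defines enrollment: "Subjects are enrolled in the TRILUMINATE Trial upon signing and dating the informed consent form". Several steps separate that date from treatment. Under Protocol 5.1, "Any patient data transmitted from their institution to the ECL or Sponsor must have prior signed and dated informed consent". Under Protocol 3.0, only after the Eligibility Committee has confirmed eligibility is it the case that "the subject may be scheduled for the TVRS procedure".

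Other parts of the plan use the procedure as the origin:

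- Protocol 6.5: "Follow-up visits will be calculated from the date of the Procedure".
- Protocol Summary, primary safety endpoint: "Major Adverse Events (MAE) occurring after femoral vein puncture".
- SAP 1.3.2.5 divides device- or procedure-related adverse events into "those that occur within 30 days of the procedure and those that occur after 30 days of the procedure".
- SAP 1.3.1 sets the effectiveness endpoint at 30 days after the procedure.

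SAP 2.1.4 assigns Kaplan-Meier estimation as follows: "For analyses of clinical events (e.g. MAE) beyond 30-day follow-up". It gives a censoring rule but no start date. SAP 2.2.1.2 gives Kaplan-Meier with Greenwood limits and the 39% goal for 6-month MAE, also without a start date.

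**The concern.** Two clocks are in use, and the one written down for event rates is not the one on which the endpoints are built. The 2.1.2 sentence governs any 30-day rate without a clock of its own: MAE, major bleeding and pulmonary thromboembolism.

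If MAE can occur only after femoral vein puncture, the days between consent and procedure contribute no possible events, and the same number of days is lost from the end of the window. In treated subjects the rate can then only be biased downwards, which favours the device.

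The primary safety test is exposed in a weaker sense. It has no visible origin of its own, and the only event-rate origin in the readable SAP is the enrollment sentence. A programmer might carry it over. That is an inference, not something the SAP states.

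The direction is not fixed for outcomes without a puncture rule, such as all-cause mortality. Nor is it fixed if pre-procedure events can count as MAE, which the SAP's own definition in 1.3.1 does not rule out because it omits the puncture rule.

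**Working it through.** The plan gives no figure that depends on the time origin, so there is nothing to reproduce. The check has three steps.

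**1. Can enrollment coincide with the procedure?** The protocol words enrollment in three ways: consent (5.3), eligible and consented (3.1), and, by implication, the Eligibility Committee's decision (11.8.4). All three precede the procedure, because scheduling follows the committee's confirmation (3.0). The second and third shorten the gap but do not close it.

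**2. 30-day rates.** Let L be the lag in days from enrollment to procedure. L is an assumption because the screening window is not visible. The window covers 30 − L post-procedure days. The share of 30-day events kept is (30 − L)/30 if events are evenly spread, or √((30 − L)/30) under an assumed front-loaded pattern (Weibull shape 0.5).

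| L (days) | Days covered | Kept, even | Kept, front-loaded |
|---|---|---|---|
| 7 | 23 | 77% | 88% |
| 14 | 16 | 53% | 73% |
| 30 | 0 | 0% | 0% |

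**3. 6-month MAE test, only if the consent clock is applied there.** Inputs are N = 85 (Protocol 5.7), goal 39% (SAP 2.2.1.2) and one-sided 2.5% (SAP 2.6). Assumptions are no censoring and 6 months = 180 days.

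*Pass rule.* Without censoring, Greenwood's standard error is √(p(1 − p)/85).

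- Linear limit: 24 events give 0.2824 + 1.96 × 0.0488 = 0.378, and 25 give 0.391, so the trial passes at 24 or fewer.
- Log-log limit: 23 events give 0.3785 and 24 give 0.391, so it passes at 23 or fewer. SAP 2.2.1.2 does not say which form is used.

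*Counted rate.* With true 6-month rate p₀ and H = −ln(1 − p₀):

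- constant hazard: p(L) = 1 − exp(−H(180 − L)/180)
- front-loaded: p(L) = 1 − exp(−H√((180 − L)/180))

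For p₀ = 0.39, H = 0.494. Example at L = 30, constant hazard: 1 − exp(−0.494 × 150/180) = 0.338. Pass probabilities are binomial, P(X ≤ 24) or P(X ≤ 23).

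| L (days) | Counted rate (constant / front-loaded) | False pass, linear (constant / front-loaded) | False pass, log-log (constant / front-loaded) |
|---|---|---|---|
| 0 | 0.390 / 0.390 | 2.5% / 2.5% | 1.4% / 1.4% |
| 7 | 0.378 / 0.384 | 4.2% / 3.3% | 2.5% / 1.9% |
| 14 | 0.366 / 0.378 | 6.6% / 4.2% | 4.1% / 2.5% |
| 30 | 0.338 / 0.363 | 16.8% / 7.4% | 11.5% / 4.6% |

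At a true rate of 20%, the pass probability with the linear limit is 97.5% at L = 0. At L = 30 it is 99.7% (constant hazard) or 99.1% (front-loaded).

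**The case against.** The strongest reply concerns scope. The sentence sits in a section on descriptive statistics for categorical variables, with 30 days as its example. SAP 2.1.4 moves later events to Kaplan-Meier, and nothing visible ties the enrollment clock to the primary safety test. SAP 1.4 is not readable, and SAP 2.1.3, SAP 2.5 and Protocol section 9 are not in the text we have, so an origin may be stated there. This stands: the 6-month part is a request for a stated origin, not a demonstrated error in the test. An origin in unseen text would not remove the contradiction in 2.1.2.

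Second, the downward direction needs the after-puncture rule, which is stated for the whole composite only in the Protocol Summary. Protocol 4.2 and SAP 1.3.1 omit it. This also stands, so the direction is conditional on that rule.

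Third, the size rests wholly on an assumed lag. A 30-day lag is an extreme that would be obvious in any output, and the front-loaded pattern is not a bound: if events cluster in the first days after the procedure, a 7- or 14-day lag loses few. With a log-log limit, a 7-day lag does not raise the false-pass rate above the nominal 2.5%. All true, and these points limit the likely size.

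Fourth, much is unaffected. The effectiveness endpoint and related adverse events have their own procedure clock, and secondary analyses are descriptive. That bears on importance, not on whether the sentence is right.

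**Conclusion.** The concern holds. Followed literally, SAP 2.1.2 yields 30-day event rates with fewer than 30 post-procedure days at risk, on a different clock from the 30-day visit and echocardiogram. This is a conflict in the written rule and does not depend on which of the protocol's wordings of enrollment is used.

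The size depends on the lag. Under the two event patterns considered, a lag of 7 to 14 days would lose roughly 12% to 47% of 30-day events, taking MAE as limited to events after puncture.

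For the primary safety test, the firm finding is that no time origin is visible. Inflation of the false-pass rate arises only if the consent clock is carried over. It is modest at short lags, material at 30 days, and calculated at a true rate of exactly 39%. At a true rate of 20% the pass decision would be unlikely to change. This should be fixed before analysis, but it does not threaten the design.

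**What to change.** State in SAP 2.1.2, 2.1.4 and 2.2.1.2 that day 0 for event rates and Kaplan-Meier analyses is the index TVRS procedure (femoral vein puncture), and that 30 days and 6 months are counted from that date. Add the after-puncture rule to the MAE definition in SAP 1.3.1. Report events between consent and procedure in a separate listing. While editing, align the timing words for the surgery component in the Protocol Summary and Appendix II with the same rule; this is a minor tidying point.

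The cost is a few sentences in the SAP, matching MAE wording in the protocol and one extra listing. No new data are needed: visits already run from the procedure date (Protocol 6.5), and adverse events are already collected from enrollment (Protocol 7.3.1). The reported MAE rate may be less favourable, by an amount that depends on the actual lag.

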2.1.4 Survival Analyses

Survival analysis will be conducted to analyze time-to-event variables, e.g. all-cause mortality. For analyses of clinical events (e.g. MAE) beyond 30-day follow-up, Kaplan-Meier¹¹ estimate will be utilized.

Subjects without events will be censored at their last known event-free time point. Survival curves will be constructed using Kaplan-Meier estimates. Summary tables for endpoints will include failure rates (Kaplan-Meier estimates), and confidence interval for the failure rates.

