1. CARDIOVASCULAR DEATH (VARC)

Per the Valve Academic Research Consortium (VARC)⁵ as any one of the following:

- Any death due to proximate cardiac cause (e.g. MI, cardiac tamponade, worsening heart failure)
- Unwitnessed death and death of unknown cause
- All procedure-related deaths, including those related to a complication of the procedure or treatment for a complication of the procedure
- Death caused by non-coronary vascular conditions such as cerebrovascular disease, pulmonary embolism, ruptured aortic aneurysm, dissecting aneurysm, or other vascular disease

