2. NON-CARDIOVASCULAR DEATH

Any death not covered by the VARC definitions of Cardiovascular Death, such as death caused by infection, malignancy, sepsis, pulmonary causes, accident, suicide, or trauma.

DEVICE EMBOLIZATION

Detachment of the deployed TVRS Clip from the tricuspid leaflets as assessed by the study site.

Diagnosis and management of any occurrence or suspected occurrence of device embolization will be per the site investigator's best medical judgment. Some recommendations for clinical diagnosis and management of device embolization include but are not necessarily limited to those outlined below:

- Diagnosis:
 - Observation of patient's clinical symptoms,
 - o Assessment of Clip status via TTE examination of valve, and/or
 - Fluoroscopy and/or x-ray imaging.
- **Management** will depend on the specific patient's clinical situation and will be determined by the site investigator's best medical judgment including assessment of overall risks and benefits of further intervention. Some methods of management to consider are:
 - o Continued regular clinical monitoring of the patient and the embolized device;
 - Transcatheter manipulation method(s) to stabilize device position;

(Version 2.0; 01 February 2018)

- Removal through percutaneous approach and/or
- o Removal through surgical approach.

DEVICE THROMBOSIS

Formation of an independently moving thrombus on any part of the TVRS Clip evidenced by echocardiography or fluoroscopy. If the TVRS Clip is explanted or an autopsy is performed, this diagnosis should be confirmed.

ENDOCARDITIS

A diagnosis of endocarditis based on the following Duke criteria, from The ACC/AHA Guidelines for the Management of Patients with Valvular Heart Disease, JACC, Vol 32, No.5,November 1, 1998:pg1541, Table 21)

Endocarditis is based on the confirmation of either Pathological Criteria or Clinical Criteria.

Diagnosis for Clinical Criteria of Endocarditis must at least meet 1 of the following combinations:

- 2 major criteria or
- 1 major plus 3 minor criteria or
- 5 minor criteria

Pathological Criteria

Microorganisms: culture or histology in a vegetation, in a vegetation that has embolized, or in an intracardiac abscess, OR

Pathological lesions: vegetation or intracardiac abscess present, confirmed by histology showing active endocarditis

OR

Clinical Criteria

Major Criteria

Persistently positive blood cultures:

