1.3.2.3 Clinical Components Endpoints

- Clinical Endpoints will be assessed at 30 days, 6 months, 1 year, 2 years and 3 years:
 - Components of MAE
 - All-cause mortality
 - NYHA Functional Class
 - o Tricuspid valve surgery (including type of surgery),
 - New use of any cardiac rhythm management devices (Pacemakers, ICDs, and CRT), including reason for intervention
 - Additional TVRS intervention and reason for intervention
- Additional Clinical Endpoints:
 - Mode of Clip anchoring of coapted leaflets (anterior, posterior and/or septal) at procedure
 - Major bleeding at 30 days
 - Pulmonary Thromboembolism at 30 days
 - New Onset Renal Failure at 30 days and 6 months
 - New Onset Liver Failure at 30 days and 6 months
 - New onset atrial fibrillation at 30 days, 6 months and 1 year.
 - Change in diuretic(s) used at 30 days, 6 months, and 1 year (as compared to

baseline)

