2.2.2 Secondary

Endpoint Analyses

Analyses of secondary endpoints will be descriptive in nature and will be performed using the methods described in Section 2.1 for both the PAP and PTE populations.

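### As SAP 2.1.4 reads, deaths without the event are censored, so Kaplan-Meier failure rates after 30 days for events other than all-cause death overstate the share of patients affected: little at 6 months, more by 3 years

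*SAP*

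**What the plan says.** SAP 2.1.4 assigns Kaplan-Meier to clinical events beyond 30 days, with MAE as its example. Its only censoring rule is "Subjects without events will be censored at their last known event-free time point". On reporting it says: "Summary tables for endpoints will include failure rates (Kaplan-Meier estimates), and confidence interval for the failure rates". No visible text mentions competing risks, cumulative incidence or a separate handling of death.

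SAP 1.3.2.3 sets the horizon for the MAE components, tricuspid valve surgery, additional TVRS intervention and new rhythm devices: "Clinical Endpoints will be assessed at 30 days, 6 months, 1 year, 2 years and 3 years". Two events stop earlier: "New onset atrial fibrillation at 30 days, 6 months and 1 year", and liver failure at 6 months.

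Three other provisions bear on the point:

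- SAP 2.1.2 plans counts as well: "For categorical variables such as gender, MAE, results will be summarized with subject counts and percentages/rates".
- SAP 2.2.2 limits the purpose: "Analyses of secondary endpoints will be descriptive in nature".
- Protocol Appendix II counts "Unwitnessed death and death of unknown cause" as cardiovascular. Non-cardiovascular death is the remainder: "Any death not covered by the VARC definitions of Cardiovascular Death". Of all deaths, MAE includes only the cardiovascular ones.

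**The concern.** A patient who dies without a stroke is a patient without that event, so the rule as written censors at death. Censoring treats the patient as still able to have the stroke later. One minus Kaplan-Meier then estimates the risk as if death did not intervene. It equals or exceeds the share who actually had the event, and exceeds it as soon as any event follows a competing death.

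For MI, stroke, renal failure, endocarditis requiring surgery, non-elective CV surgery, tricuspid valve surgery, additional TVRS intervention, new rhythm device, atrial fibrillation and liver failure, every death that is not itself the event competes. For cardiovascular mortality and composite MAE, only non-cardiovascular death competes.

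Readers will take a failure rate as the proportion of treated patients who had the event. In a population with substantial mortality, the 1- to 3-year safety tables could overstate that proportion.

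**Working it through.** The visible documents state no expected event rate or competing-risk figure, so there is no figure of the plan's own to reproduce.

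**Inputs**

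- n = 85, the minimum in SAP 1.3.
- Annual mortality m = 10%, 20% and 35% (assumed). The ends are the complements of the one-year survival figures in Protocol 15.1: 90% without TR and 65% with severe TR. The top value is an upper scenario. The trial also admits moderate TR and excludes non-cardiac life expectancy under 12 months, and 35% a year for 3 years means 1 − 0.65³ = 72.5% dead.
- Annual event rate p = 2%, 5% and 10% (assumed).
- Constant hazards and no other censoring (assumed).

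**Formulas**

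- h = −ln(1 − p); μ = −ln(1 − m)
- Kaplan-Meier failure: 1 − exp(−ht)
- Cumulative incidence: [h/(h+μ)] × [1 − exp(−(h+μ)t)]
- Greenwood standard error of the Kaplan-Meier rate: exp(−ht) × √{ [h/(n(h+μ))] × [exp((h+μ)t) − 1] }

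**Worked case: p = 10%, m = 20%, t = 3 years**

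h = 0.1054, μ = 0.2231, sum 0.3285.

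- Kaplan-Meier: 1 − 0.9³ = 27.1%.
- Cumulative incidence: 0.3208 × (1 − 0.3732) = 20.1%.
- Gap: 7.0 points.
- Standard error: 0.729 × √[(0.3208/85) × 1.679] = 5.8 points.

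**All nine scenarios at 3 years** (last column: half of the 3-year event hazard moved into the first 30 days)

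| Event rate | Mortality | Kaplan-Meier | Cumulative incidence | Gap / SE | Gap / SE, early events |
|---|---|---|---|---|---|
| 2% | 10% | 5.9% | 5.1% | 0.8 / 2.8 | 0.4 / 2.7 |
| 2% | 20% | 5.9% | 4.3% | 1.6 / 3.0 | 0.8 / 2.8 |
| 2% | 35% | 5.9% | 3.3% | 2.6 / 3.7 | 1.4 / 3.2 |
| 5% | 10% | 14.3% | 12.3% | 2.0 / 4.1 | 1.0 / 4.0 |
| 5% | 20% | 14.3% | 10.5% | 3.8 / 4.5 | 2.0 / 4.2 |
| 5% | 35% | 14.3% | 8.1% | 6.1 / 5.5 | 3.2 / 4.8 |
| 10% | 10% | 27.1% | 23.4% | 3.7 / 5.3 | 1.9 / 5.1 |
| 10% | 20% | 27.1% | 20.1% | 7.0 / 5.8 | 3.5 / 5.4 |
| 10% | 35% | 27.1% | 15.7% | 11.4 / 7.0 | 5.8 / 6.1 |

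Three of the nine gaps exceed one standard error and none reaches 1.96. With early events, none exceeds one.

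**Earlier visits, constant hazards.** The gap is at most 0.5 points at 6 months (the last visit for liver failure) and 0.1 to 1.8 at 1 year (the last for atrial fibrillation).

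**Cardiovascular mortality.** With assumed rates of 8%, 20% and 30% a year and non-cardiovascular mortality of 2% to 5%, the 3-year figures are 22.1% against 21.5% to 20.6%, 48.8% against 47.5% to 45.6%, and 65.7% against 64.1% to 61.7%. Every gap is below one standard error. The rates also fail to add up. At 20% cardiovascular and 5% non-cardiovascular, 3-year all-cause mortality is 1 − 0.8³ × 0.95³ = 56.1%, yet the two cause-specific Kaplan-Meier rates sum to 48.8% + 14.3% = 63.1%.

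**Composite MAE.** With h = −ln(1 − p₆)/0.5, where p₆ is the 6-month rate, and non-cardiovascular mortality of 2% to 5% a year, a Kaplan-Meier rate at the 39% goal corresponds to a cumulative incidence of 38.8% to 38.5% at 6 months. If p₆ = 10%, the 3-year figures are 46.9% against 45.6% to 43.8%.

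**The case against.** Several points on the other side stand.

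- **Scope is partly a reading.** SAP 2.1.4 names only all-cause mortality and MAE as examples. That its phrase on clinical events covers the components and the other events is the natural reading, but still a reading. SAP 2.2.2 sends secondary endpoints to all of Section 2.1, including the counts and percentages of 2.1.2.
- **The share affected may be shown anyway.** If 2.1.2 is applied beyond 30 days, the number with the event will appear in the tables. A reader might infer that the plan hides this number; the text does not support that. Crude percentages do not handle withdrawal, however, and 2.1.2 does not displace the Kaplan-Meier rule.
- **Some text cannot be seen.** SAP 2.1.3, 2.5, the content of 1.4 and the table mockups are not visible, and any of them might deal with deaths. The point is conditional for that reason.
- **The gap is modest against the right yardstick.** The standard error of a simple proportion at the lower cumulative incidence would make the gap look larger. The fair comparison is the Greenwood error of the rate that the SAP will report, which is wider because deaths are censored. The largest gaps also need high mortality sustained for 3 years.

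It is also tempting to infer that the primary safety conclusion is at risk. The documents do not support this: non-cardiovascular death alone competes with MAE, the horizon is 6 months, and the error raises the MAE rate against the 39% goal.

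The mechanism itself survives. The overstatement always runs in one direction and grows with follow-up, unlike sampling error.

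**Conclusion.** The point holds as a minor one, provided that no unseen text already handles death. Followed as written, SAP 2.1.4 overstates the share affected for the listed events and for cardiovascular mortality. All-cause mortality is unaffected.

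Under the assumed rates the overstatement is negligible at 6 months and small at 1 year. At 3 years it ranges from trivial for rare or mostly early events to several points for commoner events under high mortality. All sizes rest on assumed rates, and the 3-year ones change with the timing of events.

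The primary 6-month MAE rate moves by about 0.5 points at most with non-cardiovascular mortality of 2% to 5% a year. At an assumed 15% a year the shift at the 39% goal would be 1.4 points. Either way it makes a pass harder, not easier. Secondary analyses are descriptive and the error is towards more harm, so this improves the 1- to 3-year reporting and does not threaten the trial's main result.

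**What to change.** Amend SAP 2.1.4 as follows:

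- Keep Kaplan-Meier for all-cause mortality and for composite MAE beyond 30 days, including the primary 6-month analysis. Leave the discharge and 30-day analyses unchanged.
- For the other clinical events beyond 30 days, report Aalen-Johansen cumulative incidence. The competing event is any death not itself adjudicated as that event; for cardiovascular mortality it is non-cardiovascular death. A fatal MI or fatal stroke counts as the event, in line with the Appendix II definitions.
- Censor at last contact only patients who are alive and event-free, including those who withdraw.
- Add the cumulative incidence of MAE, with non-cardiovascular death competing, as a supplementary result at 1, 2 and 3 years.
- Beside each rate show the numbers with the event, dead without it, and censored.

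The cost is SAP wording and a small amount of standard programming. Deaths are already recorded, and Protocol Appendix II already classifies them, so no new data are needed. The drawback is less direct comparability with published Kaplan-Meier rates, which can be kept in a supplementary table. If text not visible already treats death this way, no change is needed.
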